### **6.4 Subgroups**

If applicable, the HF20 Sets with lower clearance specifications (KUrea = 25.5 mL/min +/- 10%) and the HF20 Sets with higher clearance specifications (KUrea = 30 mL/min +/- 10%), will be considered as two subgroups for the analysis of BUN reduction.

### 7. STATISTICAL ANALYSIS

### 7.1 General/Types of Analyses

Unless otherwise noted, all analyses will be performed using SAS/GRAPH® 9.4 software, SAS/STAT® 14.1 software and Base SAS® 9.4 software. Copyright© SAS Institute Inc. SAS and all other SAS Institute Inc. product or service names are registered trademarks or trademarks of SAS Institute Inc., Cary, NC, USA. All Rights Reserved.

Unless otherwise specified, treatment effects will be evaluated on the basis of a 2-sided significance level of 0.050 (when rounded to three decimal places).

### 7.2 Handling of Missing Data

The sensitivity analyses will be performed using a multiple imputation approach. Multiple imputations using SAS PROC MI will be implemented to impute missing data under the missing at random assumption and the data sets generated will be analyzed using SAS PROC MIANALYZE.

The multiply imputed data sets are then analyzed by using standard procedures for complete data and combining the results from these analyses. Multiple imputation does not attempt to estimate each missing value through simulated values, but rather to represent a random sample of the missing values. This process results in valid statistical inferences that properly reflect the uncertainty due to missing values.

Multiple imputation inference involves three distinct phases:

- 1. The missing data are filled in m times to generate m complete data sets.
- 2. The m complete data sets are analyzed by using standard procedures.
- 3. The results from the m complete data sets are combined for the inference.

The MI procedure is a multiple imputation procedure that creates multiply imputed data sets for incomplete p-dimensional multivariate data. It uses methods that incorporate appropriate variability across the m imputations. The imputation method of choice depends on the patterns of missingness in the data and the type of the imputed variable.

Twenty (20) complete data sets based on the Markov chain Monte Carlo (MCMC) method with pre-specified covariates (age and gender) will be analyzed for the multiple imputation of the primary endpoint data as sensitivity analysis.

Three additional imputation approaches will be carried out:

- 1. Imputing the mean of the available data.
- 2. Imputing the missing values by estimating the values from a linear regression on the available data.
- 3. Imputing by worst-case approach, using the smallest observed reduction from baseline to 24 hours in BUN measurement.

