### 5.2 Sample Size

The sample size calculation is based on the primary objective of 24hours BUN reduction. It is anticipated that the true mean reduction at 24 hours will be some 62%, as would be obtained from a patient with initial BUN of 80 mg/dL and reaching 30 mg/dL after 24 hours of treatment. Data from the earlier M-10 study suggest that the standard deviation in the BUN reduction is about 45%.

Under these assumptions, the sample size needed to obtain 80% power is 24, as reported by SAS PROC POWER.

A target sample size of up to 30 patients is therefore proposed to allow for a possible 20% loss of data between the baseline and 24 hours mark.

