### **5.5 Efficacy Measures**

### **5.5.1 Primary Efficacy Measures**

The primary efficacy endpoint is the change from baseline in BUN evaluated at 24 hours following initiation of CRRT with the Prismaflex HF20 Set. BUN is to be measured at the start of CRRT treatment with the Prismaflex System, specifically BUN measurements will be taken no earlier than one hour prior to the start of CRRT and no later than 15 minutes after the start of CRRT. BUN will also be measured at 24 hours after initiation of CRRT. More specifically, BUN will be measured no later than one hour after 24 hours past CRRT initiation (25 hours treatment mark) and no sooner than one hour before 24 hours after CRRT initiation (23 hours mark). Change in baseline of BUN to 24 hours after CRRT initiation will be calculated as a percentage using the following equation:

$$\Delta BUN = \frac{BUN_{0hr} - BUN_{24hr}}{BUN_{0hr}} \times 100\%$$

Where BUNohr is BUN recorded at baseline and BUN24hr is BUN recorded at 24 hours after CRRT initiation.

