### 12. EFFICACY PARAMETERS

### 12.1 Primary Analysis

The primary analysis will be to demonstrate a mean reduction of greater than 38% in BUN at 24 hours from initiation of CRRT. This percentage of reduction is motivated by

the target of getting patients with an initial BUN of 80 mg/dL below 50 mg/dL after 24 hours of treatment.

The hypothesis to be tested is:

$$H_0$$
:  $\mu \leq 38\%$ ,

$$H_a$$
:  $\mu > 38\%$ 

Where  $\mu$  stands for the mean percentage reduction in BUN from baseline to 24 hours calculated as:

$$\mu = \frac{BUN_{0hr} - BUN_{24hr}}{BUN_{0hr}} \times 100\%$$

Where BUNohr is BUN recorded at baseline and BUN24hr is BUN recorded at 24 hours after CRRT initiation.

This hypothesis will be tested using a one-sample t test and the actual mean percentage reduction in BUN will be quantified using a 95% confidence interval.

As a supportive analysis, an analysis of variance (ANOVA) will be implemented to investigate the mean change from baseline among the different sites.

A box plot will also be generated to represent the 24 hours change in BUN from baseline.

The primary analysis of the primary endpoint will be based on the FAS. As supportive analysis, the same analysis will be carried out on the PPS.

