### 12.2 Sensitivity Analysis

The analysis of the primary endpoint using the PPS will be considered as a part of sensitivity analyses.

Subgroup analysis (if applicable) will be also considered as a part of sensitivity analyses.

The impact of missing data on the primary analysis will be further explored as sensitivity analyses using statistical imputation approaches. (See Section 7.2 for explicit details.)

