# 2. LIST OF TABLES, FIGURES AND LISTINGS

Table Number	Table Name
Table 14.1.1	Subject Disposition All Subjects
Table 14.1.2	Protocol Deviations
Table 14.1.3	Demographic and Baseline Characteristics
Table 14.1.4	Baseline Lab Values
Table 14.1.5	Baseline Vital Signs
Table 14.1.6	Treatment Exposure Full Analysis set / Per Protocol Set
Table 14.2.1	Laboratory Efficacy Response Percent Change from Baseline to 24 Hours Full Analysis Set / Per Protocol Set
Table 14.2.1.1	Laboratory Efficacy Response Percent Change from Baseline to 24 Hours for Sensitivity Analysis Based on Clearance Specification Subgroup Full Analysis Set / Per Protocol Set
Table 14.2.1.2	Laboratory Efficacy Response Percent Change from Baseline to 24 Hours with Missing Data Imputations Full Analysis Set
Table 14.2.2	Laboratory Efficacy Response Change from Baseline to 24 Hours (ANOVA) Full Analysis Set / Per Protocol Set
Table 14.2.2.1	Laboratory Efficacy Response Change from Baseline to 24 Hours for Sensitivity Analysis Based on Clearance Specification Subgroup (ANOVA) Full Analysis Set / Per Protocol Set
Table 14.2.2.2	Laboratory Efficacy Response Change from Baseline to 24 Hours with Missing Data Imputations (ANOVA) Full Analysis Set
Table 14.2.3	HF20 Set Filter Life Survival Analysis Full Analysis Set / Per Protocol Set
Table 14.2.3.1	HF20 Set Filter Life Cumulative Survival Rate Full Analysis Set
Table 14.2.3.2	HF20 Set Filter Life Cumulative Survival Rate Per Protocol Set
Table 14.2.4.1	Relationship Between BUN and Creatinine Clearance Rate and Characteristic Variables Full Analysis Set
Table 14.2.4.2	Bicarbonate Analysis of Variance Full Analysis Set
Table 14.3.1.1	Number of Subjects with At Least One Adverse Event (Serious and Non-Serious) Full Analysis Set
Table 14.3.1.2	Number of Adverse Events (Serious and Non-Serious) Full Analysis Set
Table 14.3.1.3	Number of Subjects with at Least One Adverse Event (Serious or Non-Serious) by System Organ Class and Preferred Term Full Analysis Set
Table 14.3.1.4	Number of Subjects with at Least One Serious Adverse Event by System Organ Class and Preferred Term Full Analysis Set
Table 14.3.1.5	Number of Adverse Events (Serious or Non-Serious) by System Organ Class and Preferred Term Full Analysis Set
Table 14.3.1.6	Number of Serious Adverse Events by System Organ Class and Preferred Term Full Analysis Set

Table Number	Table Name

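### None of the planned missing-data analyses of the primary BUN endpoint is specified to use the 12-hour BUN; the multiple imputation names only age and gender

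*SAP*

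**What the plan says.** SAP 12.1 tests the mean percent reduction in BUN at 24 hours against 38% with a one-sample t test, and states: "The primary analysis of the primary endpoint will be based on the FAS". That set includes any child treated on the HF20 Set for any length of time (SAP 6.2). SAP 12.1 attaches no imputation to the test, so a child without a 24-hour BUN cannot contribute to it.

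SAP 12.2 handles missing data separately: "The impact of missing data on the primary analysis will be further explored as sensitivity analyses using statistical imputation approaches". The results have their own table, 14.2.1.2 in the second list of tables: "Laboratory Efficacy Response Percent Change from Baseline to 24 Hours with Missing Data Imputations Full Analysis Set".

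SAP 7.2 gives four methods:

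- Multiple imputation under missing at random: "Twenty (20) complete data sets based on the Markov chain Monte Carlo (MCMC) method with pre-specified covariates (age and gender) will be analyzed".
- Imputation of the mean of the available data.
- Single regression imputation: "Imputing the missing values by estimating the values from a linear regression on the available data".
- A worst case: "Imputing by worst-case approach, using the smallest observed reduction from baseline to 24 hours in BUN measurement".

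BUN is scheduled at baseline and every 12 hours on treatment (Protocol Table 1, SAP Table 2). SAP 5.1 says these values are taken for statistical analysis.

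**The concern.** Multiple imputation is a useful check only if its model holds variables that predict the missing value or the loss. Age and gender may predict neither. The obvious candidate is the same child's 12-hour BUN, and nothing in SAP 7.2 calls for it. Whether baseline BUN enters is not stated either.

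The documents describe how a child can have a 12-hour value and no 24-hour value. Under Protocol 3.2, a child who no longer needs CRRT before 24 hours is withdrawn and needs no more study samples. Protocol 4.5 also withdraws children for interruptions or need of another filter, and SAP 5.8 lists lack of efficacy as a reason. Some of these routes could remove fast responders and others slow ones, so the direction of any bias is unknown.

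At stake is false reassurance. If loss tracks early response, the available-case mean and the multiple imputation would agree closely and both be wrong by the same amount. The planned 12-hour summaries and listings (Protocol Appendix 1, SAP 13.3) would show the lost children's early values but would not turn them into an estimate.

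**Working it through.** **Inputs from the plan.** Mean reduction 62, null value 38, N = 24 for 80% power, 20% loss, target 30 (SAP 5.2, 12.1). For the spread: "Data from the earlier M-10 study suggest that the standard deviation in the BUN reduction is about 45" percent.

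**The plan's own figure.** Difference 62 − 38 = 24; noncentrality (24/45)·√24 = 2.61. The exact t test at one-sided 0.05 gives N = 24 with power 81.3%, which matches. At two-sided 0.05, the default in SAP 7.1, power at 24 is 70.6%. Inflation 24/(1 − 0.20) = 30 also matches, so the plan expects 30 − 24 = 6 children without a 24-hour value.

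**Why the planned imputation returns the completers' mean.** If age and gender do not predict the reduction, the imputed values average the completers' mean m. The result is then (24m + 6m)/30 = m.

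**Simulation.** Assumptions not in the documents:

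- normal responses;
- 12-hour/24-hour correlation r of 0.5 or 0.8;
- 6 of 30 lost by weighted sampling, log-weight 1.0 per SD of 12-hour response;
- age, gender and baseline BUN unrelated to outcome;
- every lost child has a 12-hour value.

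Twenty imputations, Rubin's rules, 3000 to 4000 trials per row, mean 62, SD 45:

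| Lost | r | Truth | Completers | MI: age, gender | MI: plus baseline and 12-hour BUN |
|---|---|---|---|---|---|
| Slow responders | 0.5 | 62.2 | 66.4 | 66.4 | 62.2 |
| Slow responders | 0.8 | 61.8 | 68.7 | 68.7 | 61.8 |
| Fast responders | 0.5 | 62.1 | 57.9 | 57.9 | 62.1 |
| Fast responders | 0.8 | 62.0 | 55.2 | 55.3 | 62.0 |

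The error is 4.2 to 6.9 points. In the first row the lost children average (30 × 62.2 − 24 × 66.4)/6 = 45.4.

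**How the size moves.** The error is 3.3 to 5.5 points at log-weight 0.75 and 5.4 to 8.8 at 1.5. A normal distribution with mean 62 and SD 45 puts 20% of values above the possible maximum of 100%, so SD 20 is an alternative: the error is then 1.9 to 3.1 points at log-weight 1.0. With random loss, completers and both imputations are within 0.1 of the truth.

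**Error rate at the null.** With true mean 38, slow responders lost at log-weight 1.5, SD 45 and a one-sided 0.05 test, the age/gender imputation rejects in 13.6%, 20.8% and 29.9% of trials for r = 0.5, 0.7 and 0.9. With the 12-hour value added, it rejects in 5.0% to 5.2%.

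**Limits of the remedy.** If half of the lost children lack a 12-hour value, about 55% of the error is removed; if all lack it, none is. If loss depends on the 24-hour response itself, about 22% (r = 0.5) to 60% (r = 0.8) is removed.

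**Mean imputation.** It returns the completers' mean exactly, but its standard error is √[(23/29)(24/30)] = 0.797 times the available-case one. At SD 45 that is 0.797 × 9.2 = 7.3. With random loss it passes in 84% of trials against 71% for available cases (two-sided 0.05). At a true mean of 38 its upper-tail error is 5.8% against 2.5%. At one-sided 0.05 the figures are about 89% against 81%, and 9.5% against 5.0%.

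**Distance from reversal.** With completers at 62, the lost children would have to average (30 × 38 − 24 × 62)/6 = −58% to bring the full-set mean to 38%. Two-sided significance would be lost if they averaged below about 26% at SD 45, or about −21% at SD 20, each SD held fixed.

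**The case against.** The strongest reply is that the risky direction is already covered. Only loss of slow responders could falsely support the claim, and the worst-case imputation guards against that. With slow responders lost (log-weight 1.0 and 1.5, r 0.5 and 0.8) it averages about 49 to 55 at SD 45 and 56 to 59 at SD 20, against a truth of about 62. The completers average 66 to 71 and 64 to 66. So the planned set brackets the truth on average, and loss of fast responders is conservative for the test. This stands, and it is a main reason the point is minor. But a bound is not an estimate: under random loss the same method gives 44.2 to 44.7.

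Second, the text is partly silent rather than wrong. The regression could be programmed with the 12-hour BUN, and age and gender might be additional to the BUN variables. That is possible, but SAP 3 says the plan is to guide programming, and open predictors leave the choice until after the data are seen.

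Third, the exploratory sections are blank in the public text, and Table 14.2.4.1 shows that a further BUN analysis exists. Other uses of serial BUN therefore cannot be excluded, and the blanks are not counted against the plan. Nothing visible links them to the missing-data analyses.

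Fourth, correlation, loss mechanism and availability of 12-hour values are all assumed. Some withdrawals, such as those for filter type, need not track urea removal, and end-of-study data are sought where possible (Protocol 3.2, SAP 5.8). All true; the size is illustrative only.

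**Conclusion.** The concern holds, as a minor improvement to a sensitivity analysis. As written, the multiple imputation conditions on age and gender only, and no method is specified to use the 12-hour BUN.

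If loss depends on 12-hour response and age, gender and baseline BUN are not predictive, the planned imputation carries the same error as the analysis it is meant to test: roughly 4 to 7 points at the plan's SD, and 2 to 3 at SD 20. The margin between the expected mean and the null is 24 points. The direction cannot be known from the documents. If loss is random there is nothing to correct, and no reversal of the 38% conclusion is shown.

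**What to change.** In SAP 7.2:

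1. Add baseline BUN and the 12-hour percent reduction in BUN to age and gender in the MCMC model. Use the SAP 5.5.1 formula with the 12-hour value in place of the 24-hour one. The percent scale is preferable: in a check with an assumed 12-hour mean of 38 and SD of 31.5, it left at most 0.13 points of error, against 0.3 to 0.7 for the 12-hour concentration.
2. Name the same predictors for the regression imputation.
3. State that children lost before 12 hours are informed by baseline data only.
4. Treat p values from mean and single regression imputation as descriptive, because their standard errors are too small. For the regression with 12-hour BUN under random loss, the standard error is 7.6 to 7.9, against 8.8 to 9.5 for multiple imputation.

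The cost is SAP wording, since the samples are already scheduled. The model gains two parameters with about 24 complete children: its standard error is 9.7 against 9.4 at r = 0.5, and 8.9 against 9.1 at r = 0.8. SAP 11 records that imputation was agreed with the FDA, so the added predictors should be communicated.

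Separately, and without bearing on this point, two sets of passages need reconciling: Protocol 3.2 (24 hours) with Protocol 4.5 and 4.6 (20 hours), and SAP 5.1 (at least 20 hours) with the full analysis set in SAP 6.2 (any duration).

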### 4.3 Exploratory Objectives

### 5. STUDY DESIGN AND CONDUCT CONSIDERATIONS

### 5.1 Study Design

The clinical study design is a multicentric, open label, single group study in which patients meeting all the inclusion criteria and none of the exclusion criteria of the study protocol, and deemed treatable by their physician with the Prismaflex HF20 Set and Prismaflex System Software Version 7.10 or with the Prismaflex HF20 Set and Prismaflex System Software Version 7.20, will be enrolled in the study. Patients included in the analysis will be treated for a minimum period of 20 of the first 24 hours and up to 72 hours with each Prismaflex HF20 Set with BUN, creatinine and bicarbonate being measured for statistical analysis at 12 hour intervals during CRRT treatment.

The duration of time for which each Prismaflex HF20 Set can be used will be evaluated out to a time period of 72 hours from the initiation of CRRT in each patient. The end of the extracorporeal circuit life will be defined by the occurrence and failure to mitigate one or both of the following Prismaflex System alarms, after which CRRT will be terminated and the extracorporeal circuit replaced:

• "Warning: Filter Clotted", and/or

• "Caution: TMP Excessive"

At 72 hours from the initiation of HF20 study CRRT, if the patient has been on the current Prismaflex HF20 Set for less than 72 hours, the patient is allowed to continue on their current filter set until the end of filter life (please refer to the study Protocol Section 3.2 for explicit detail). The site may follow applicable institutional practices if additional CRRT is required.

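### The mean fill in SAP 7.2, if put through the one-sample t test, repeats the available-case estimate with a standard error up to 20% too small; report its mean only, or drop it

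*SAP*

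**What the plan says.** SAP 12.1 tests whether the mean percentage reduction in BUN at 24 hours exceeds 38% in the full analysis set: "This hypothesis will be tested using a one-sample t test". The same section adds a supportive ANOVA across sites. No imputation is described for the primary analysis itself, so I take it to use children with both values.

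SAP 12.2 gives imputation its role: "The impact of missing data on the primary analysis will be further explored as sensitivity analyses using statistical imputation approaches". SAP 7.2 lists four approaches:

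- Multiple imputation under missing at random, with 20 MCMC data sets and age and gender as covariates, combined with PROC MIANALYZE.
- "Imputing the mean of the available data".
- "Imputing the missing values by estimating the values from a linear regression on the available data".
- "Imputing by worst-case approach, using the smallest observed reduction from baseline to 24 hours in BUN measurement".

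The SAP does not say which variable is filled in the last three, how the filled data are tested, which predictors the regression uses, or whether it adds residual draws. The later of the SAP's two table lists includes "Laboratory Efficacy Response Percent Change from Baseline to 24 Hours with Missing Data Imputations Full Analysis Set" (Table 14.2.1.2) and an ANOVA counterpart on imputed data (Table 14.2.2.2). SAP 5.2 sets the sample at up to 30 children "to allow for a possible 20% loss of data between the baseline and 24 hours mark".

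**The concern.** A sensitivity analysis should show whether the answer changes when the missing values are treated differently. A mean fill cannot do that. It places every missing child at the centre of the observed data, so the estimate stays where it was. An ordinary t test then counts the filled values as real observations and reports more precision than the data hold. Printed beside the primary result, this looks like confirmation.

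The question matters because the primary population includes any child treated on the HF20 Set for any length of time, so missing 24-hour values are to be expected. Protocol 3.2 and 4.5 tie early loss to the child's own course: CRRT no longer needed, a second interruption, or need for a non-HF20 filter. Missing at random is therefore worth probing, although the direction of any departure is unknown.

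At stake is the credibility of one sensitivity analysis, or two if the regression fill is also a single deterministic fill.

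**Working it through.** **Inputs.** Threshold 38% (SAP 12.1). True mean 62%, SD 45%, 24 evaluable children, 30 in total, 20% loss (SAP 5.2). Two-sided 0.05 as the default level (SAP 7.1).

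**The plan's own figure.** Effect 62 − 38 = 24 points, SD 45, noncentral t. At one-sided 0.05, n = 24 gives 81.3% power, which reproduces the stated 24, and 24/0.8 = 30. At two-sided 0.05 the requirement is 30, and n = 24 gives 70.6%. The documents therefore leave room for both levels, which matters in the last step.

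**Mean fill.** Let n of N values be observed, with sum of squares S about their mean. Filling N − n values with that mean changes neither the mean nor S. Hence

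- available-case SE = √[S/(n(n−1))]
- filled SE = √[S/(N(N−1))]
- ratio = √[n(n−1)/(N(N−1))]

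| Missing of 30 | Ratio | SE too small by |
|---|---|---|
| 2 | √(756/870) = 0.932 | 7% |
| 3 | √(702/870) = 0.898 | 10% |
| 4 | √(650/870) = 0.864 | 14% |
| 6 | √(552/870) = 0.797 | 20% |

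**Effect on the limit, 6 missing.** Available-case SE = 45/√24 = 9.19, and the lower limit is 62 − 2.069 × 9.19 = 43.0%. Filled SE = 9.19 × 0.797 = 7.32, and the lower limit is 62 − 2.045 × 7.32 = 47.0%.

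**Effect on error.** The filled test rejects when the available-case t exceeds 0.797 × 2.045 = 1.63 on 23 df. If values are missing completely at random, the actual one-sided error is 0.058 for nominal 0.025. At nominal 0.05 it is 0.094.

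**Regression fill, only if single and without residual draws.** Simulation with one continuous and one binary covariate, normal residuals and values missing at random; R² is an assumption. The comparison is the nominal SE against the true SD of the filled mean.

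| R² | 6 missing: SE too small by | 3 missing |
|---|---|---|
| 0.3 | 15–16% | about 8% |
| 0.5 | 11–12% | about 6% |
| 0.7 | 7–8% | about 4% |

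**Where the conclusion would change.** Let p be the missing share. With the SE held at its available-case value, the lower limit reaches 38% when the missing children average 62 − (24 − t × SE)/p. For 6 missing at SD 45, two-sided: 62 − (24 − 19.0)/0.2 = 37%. One-sided 0.05: 62 − (24 − 1.714 × 9.19)/0.2 = about 21%. The second figure in each range below uses Rubin's rules with 20 imputations and includes the spread that the shift adds.

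| Case | Two-sided 95% limit | One-sided 0.05 limit |
|---|---|---|
| SD 45%, 6 missing | 37 to 40% | 21 to 25% |
| SD 30% (assumed), 6 missing | 5 to 15% | −6 to 6% |
| SD 45%, 3 missing | 0 to 11% | −30 to −13% |

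**The case against.** Several points on the other side stand.

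- **The fault is conditional.** SAP 7.2 does not name the filled variable. If the mean 24-hour BUN were filled instead of the percentage reduction, the estimate would no longer equal the available-case mean exactly, and the SE ratio would differ. Filling the percentage reduction is the natural reading, because the section speaks of imputing the primary endpoint data and the table list refers to percent change.
- **The regression fill may be sound.** SAP 7.2 opens with multiple imputation as the general approach, and the regression may include residual draws. Only the mean fill is deterministic on its face.
- **The t test is not the only analysis of this endpoint.** The site ANOVA is planned too, including on imputed data. The figures above apply to the t test.
- **A harsh departure from missing at random is already planned.** At the planning values with normal data and 24 observed, the smallest observed reduction averages about −26%, well below the 21 to 40% at which the conclusion changes with 6 missing. If the worst-case fill passes, the conclusion survives a severe test. If it fails, it does not show where the change occurs, though a reader could approximate that from n, mean and SD.
- **A correctly propagated multiple imputation sits beside the mean fill**, and SAP 11 records FDA agreement to the imputation plan. Neither corrects the mean fill's error bars.

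A reader might infer that the trial's conclusion is fragile because the tipping point lies near 38%. The documents do not support that. The 37 to 40% range needs the two-sided limit, SD 45% and 6 missing together, and the other cases lie well lower.

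**Conclusion.** The point holds for the mean fill. Used with the one-sample t test on percentage reductions, it adds no information about missing data and understates the SE by 7% to 20% for 2 to 6 of 30 missing. The 20% case is the plan's own loss allowance. For the regression fill the point is conditional on a single fill without residual draws, and its size depends on an assumed R².

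A reader might infer that the primary result or its error rate is compromised, or that the plan never departs from missing at random. Neither follows. The primary test does not use these fills, the multiple imputation carries its own uncertainty, and the worst-case fill is a departure from missing at random that this point leaves untouched. The missing tipping-point analysis is a gap worth filling but not an error. The correction is worth making because a stated analysis would print wrong error bars and the remedy is nearly free.

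**What to change.** In SAP 7.2:

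1. Drop the mean fill, or report its mean without a confidence interval or p-value.
2. For the regression fill, name the predictors and run it with residual draws through the multiple imputation, or report its mean only. A natural added predictor is 12-hour BUN where available, since SAP 5.1 already has "BUN, creatinine and bicarbonate being measured for statistical analysis at 12 hour intervals during CRRT treatment".
3. State which variable is filled and which test follows.
4. Keep the worst-case fill as written.

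Optional: one table that shifts the multiply imputed reductions downward in steps and reports the average among missing children at which the lower limit reaches 38%, stating whether that limit is one- or two-sided.

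The cost is SAP wording, a little analysis work, one extra table if the option is taken, and a note to the FDA because the imputation plan was agreed with it (SAP 11). No new data are needed. The sensitivity results may look less favourable than the uncorrected fills would.
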